## 3.4 Primary endpoint/outcome

The primary outcome measure is: Treatment failure within 180 days of randomisation.

For in-patients, treatment failure is defined when a patient meets objective criteria for both inflammation and infection within a 5-day period. Meeting of the criteria for inflammation may precede or follow the date that criteria for infection were met (the first day of an eligible antibiotic treatment course). These criteria are:

Criteria for Inflammation

- A fever (≥ 37.8 degrees Celsius) or hypothermia (≤36 degrees Celsius), plus
- A neutrophilia (>7.5 x10^9/L) or neutropaenia (<1.8 x10^9/L), plus
- A CRP over 100 mg/L

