#### PLUS, criteria for infection

- Initiation of a new antibiotic treatment course of  $\geq$  5 days, or
- A change in antibiotic treatment continued for  $\geq$  5 days, or
- Initiation of a new antibiotic treatment, or a change in antibiotic treatment, and death within 5 days, or
- Bacteraemia with a recognised intestinal pathogen.

New or changed antibiotic treatments must not be antibiotic prophylaxis, a change to achieve oral administration from intravenous antibiotics only, a change to reduce the spectrum of activity (targeted antibiotic treatment) or made due to antibiotic allergy only. New/changed antibiotics can include additional antibiotics, added to an ongoing treatment regimen. The first day of an eligible new/changed antibiotic treatment is called the antibiotic reference date. Inflammation 5 days either side of this antibiotic reference date can be assessed against the criteria for inflammation. A blinded endpoint committee will assess and classify data including but not limited to inflammation and antibiotic treatments to assign participants with treatment failure.

Once discharged, treatment failure requires re-admission to hospital and the in-patient criteria above to be met. Alternatively, they must have been admitted to hospital and have consumed antibiotics for > 48 hours prior to admission. Treatment failure cannot be assigned based on inflammation (fever, neutrophilia and CRP>100mg/L) detected within the 5 days after an operative procedure (surgical or radiological). Treatment failure can be assigned based on pre-operative inflammation and post-operative antibiotic changes. Treatment failure cannot be assigned due to evidence of inflammation or infection, as defined above, within the first 5 days of antibiotic treatment for the initial cIAI. If treatment

is extended beyond the intervention duration this should be considered a new antibiotic treatment course.

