Number and type of source control procedures: In-patient operation notes and radiological reports will be monitored to determine the total number of source control procedures and their type (radiologically guided (Ultrasound scan, CT) or surgical (open, laparoscopic)). The definition of source control used for this study is any procedure that stops the ongoing contamination of the peritoneal cavity and removes the majority of the contaminated intraperitoneal contents to the extent that no further acute interventions are felt to be necessary. Depending on the site and origin of the infection, multiple techniques could be satisfactory to obtain source control. Acceptable procedures might include simple drainage via open, laparoscopic, or percutaneous means, repair of a perforated viscus, resection and primary re-anastomosis of a perforated viscus, resection of a perforated viscus and proximal diversion, or proximal diversion without resection as long as adequate drainage is obtained. Note, where the abdomen is left open following a surgical procedure a procedure to close the abdomen will be counted as a second and separate procedure,

Relapse of cIAI: In patients with an episode of treatment failure up to 180 days after randomisation, senior clinicians from the patient's primary care team will be asked to report if the patient had a relapse or not, and the date of the first relapse.

Antimicrobial resistant (AMR) infection: When standard treatment fails in patients with cIAI, antibiotics are often escalated to one of the carbapenem class of antibiotics. We will therefore use rates of carbapenem prescribing as a surrogate for AMR infections. Whilst all surrogates of AMR infection have limitations, this measure is important to both patients and clinicians and should be an effective AMR surrogate measure across a large number of sites.

Further, we will complete passive surveillance of AMR infection across the six month follow up period. Susceptibility patterns of bacterial isolates identified as part of routine clinical practice will be collated from microbiology laboratories to identify AMR including MRSA, VRE, ESBL and CPE. Detection of any AMR infection (MRSA, VRE, ESBL and CPE) will be a secondary outcome. Also, antimicrobial treatments will be analysed for the number of antibiotic class switches. We do not consider it feasible to standardise the investigation of infections for patients with acute infections to allow active surveillance of AMR.

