## 7.3 Blinding

This is an unblinded trial with both treating clinicians and participants aware of treatment allocations.

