## Relapse of cIAI

The proportion of patients that experience a relapse of cIAI during the 180 days following randomisation will be reported by randomised group. This outcome will be modelled using a mixed effect logistic regression model with fixed effects for allocation, the stratification factors and other prognostic baseline covariates, and random intercepts for study recruitment site. The estimated

conditional odds ratio for allocation, 95% confidence interval and p-value will be reported. To aid interpretability, point estimates and appropriate two-sided 95% confidence for the relative risk (cases/non-cases) and absolute risk reduction (based on the fitted model) will be reported, with the fixed effect covariates in the model set to various representative values (i.e. marginal risk ratios and risk differences at representative values). Average marginal effects on both the risk ratio and risk difference scales will also be reported with appropriate two-sided 95% confidence intervals.

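### Relapse of cIAI is ascertained only in patients already classed as treatment failures, by unblinded clinicians without stated criteria, yet is analysed as a proportion of all patients by arm

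*Protocol*

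**What the plan says.** - **Who is asked.** Section 3.6, under relapse of cIAI: "In patients with an episode of treatment failure up to 180 days after randomisation, senior clinicians from the" patient's team "will be asked to report if the patient had a relapse or not, and the date of the first relapse". No definition of relapse follows.
- **What is analysed.** Section 10.2.4: "The proportion of patients that experience a relapse of cIAI during the 180 days following randomisation will be reported by randomised group", followed by a mixed logistic model. No restriction to treatment failures is stated.
- **Who knows the allocation.** Section 7.3: "This is an unblinded trial with both treating clinicians and participants aware of treatment allocations".
- **What the blinded committee does.** Section 3.4: "A blinded endpoint committee will assess and classify data including but not limited to inflammation and antibiotic treatments", in order to assign treatment failure. Section vi gives the committee outcome review in general terms, but section 3.6 gives the relapse judgement to the treating team.
- **What it takes to be a treatment failure.** Section 3.4: "For in-patients, treatment failure is defined when a patient meets objective criteria for both inflammation and infection within a 5-day period". The inflammation limb needs abnormal temperature, abnormal neutrophils and CRP above 100 mg/L together. The infection limb needs a qualifying new or changed antibiotic (normally for at least 5 days, or with death within 5 days), or bacteraemia with an intestinal pathogen. After discharge: "Once discharged, treatment failure requires re-admission to hospital and the in-patient criteria above to be met". An alternative for patients admitted after more than 48 hours of antibiotics follows, and its wording is ambiguous.

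**The concern.** The outcome collected and the outcome analysed are not the same. A patient never assigned treatment failure is never asked about relapse, so can enter a proportion of all patients only as no relapse. Section 1 describes relapse as an event that leads to further source control, yet a recurrent collection drained at a CRP of 80 mg/L, or drained while the existing antibiotics simply continue, does not meet the failure definition.

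Two further features make this more than a uniform under-count. Entry to the question depends partly on starting or changing antibiotics, and antibiotic duration is what is randomised. The answer is then an unstructured yes or no from clinicians who know the arm.

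Relapse is a secondary outcome, but it features strongly in the rationale: section 1 cites 4/17 against 0/13 in the feasibility trial. Readers will look to it for support of the primary result. As collected, it is nested inside that result. The SAP is not at hand, but this is a data-collection rule, and no analysis plan can recover a judgement that was never requested.

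**Working it through.** **Design figure.** The only calculated figure is the sample size in section 10.1 (50% against 40%, two-sided 5%, 90% power). The pooled two-proportion formula gives

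n = [1.960 × √(2 × 0.45 × 0.55) + 1.282 × √(0.25 + 0.24)]² / 0.10² ≈ 519 per arm.

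The protocol's 524 per arm is within 1% of this and gives power 0.903. With 10% attrition, 524 / 0.9 rounds up to 583 per arm, or 1166. The figure reproduces and is not at issue. No figure is stated for relapse.

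**The gate, step by step.** A true relapse reaches the relapse question only if (1) all three inflammation criteria are met, (2) an infection criterion is met within the 5-day window, (3) the inflammation is not from the 5 days after an operative procedure, and (4) after discharge, the patient is re-admitted. Relapses failing any step are lost under this label, whatever the arm.

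**Why capture could differ by arm.** Section 1 gives, for UK practice, a median antibiotic duration of 12 days (IQR 7 to 18) and a median time to relapse of 18 days (IQR 13 to 30). Linear interpolation between the relapse quartiles gives 0.50 + 0.25 × (28 − 18)/(30 − 18) = 71% of relapses by day 28. A lognormal fit gives 76%. Both assume that the relapse and antibiotic clocks roughly coincide. Many relapses would therefore fall after a usual course has ended, when restarting treatment counts under "Initiation of a new antibiotic treatment course of" at least 5 days, but while the 28-day arm is still treated, when a qualifying change or addition is usually needed. This shows how capture could differ, not by how much.

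**Illustration.** Inputs: true relapse 17.3% in both arms (section 1) and 524 analysed per arm (section 10.1), so 524 × 0.173 ≈ 91 true relapses per arm. The capture shares are assumptions, because the protocol gives none. Recorded rate = 0.173 × capture share. The odds ratio compares the 28-day arm with control. The last column is the two-sided 5% rejection rate by normal approximation, with no true difference.

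| Capture, control / 28-day | Recorded rate, control / 28-day | Odds ratio | Rejection rate |
|---|---|---|---|
| 100% / 100% | 17.3% / 17.3% | 1.00 | 5% |
| 80% / 80% | 13.8% / 13.8% | 1.00 | 5% |
| 100% / 90% | 17.3% / 15.6% | 0.88 | 12% |
| 90% / 80% | 15.6% / 13.8% | 0.87 | 12% |
| 90% / 70% | 15.6% / 12.1% | 0.75 | 37% |
| 90% / 100% | 15.6% / 17.3% | 1.13 | 12% |
| 80% / 90% | 13.8% / 15.6% | 1.15 | 12% |
| 70% / 90% | 12.1% / 15.6% | 1.34 | 37% |

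Example, 90% / 80%: (0.1384/0.8616) / (0.1557/0.8443) = 0.1606 / 0.1844 = 0.87. A 10-point gap is about 9 relapses in one arm.

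Equal capture below 100% creates no false difference but lowers both rates. It also costs power: if relapse truly fell by a fifth (17.3% to 13.8%), power would go from 34% at full capture to 27% at 80% capture in both arms.

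**The case against.** A reader might infer that the gate tilts relapse towards the intervention, because patients still on antibiotics less often start a new course. The protocol does not support that as a fact. Section 3.4 also counts antibiotics added to an ongoing regimen. It treats an extension past the intervention duration as a new course, and only one arm has a fixed duration to exceed (sections 8.2 and 8.3). Its ambiguous route for patients admitted after more than 48 hours of antibiotics could be easier to meet for someone discharged on a 28-day course. Each of these could raise capture in the 28-day arm. The timing figures come from usual care, section 1 itself reports that longer treatment delayed relapse, and the 28-day clock generally starts before randomisation. Unblinded reporting could err either way. No single bias figure can be defended, and none is offered.

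Two other points have force. First, the clinical events do not vanish: source control procedures, re-admissions and graded complications are collected and compared for all patients. They are missing only as relapse, but relapse is the outcome that section 10.2.4 tests. Second, the gate may be deliberate, confining an unblinded opinion to episodes that a blinded committee has already assigned. That is a legitimate preference for specificity, but it then defines a different outcome from the one analysed, and the opinion inside the gate remains unblinded and without criteria.

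**Conclusion.** The point holds as a defect in how a secondary outcome is collected and named. Three parts rest on the text alone: relapse is sought only among treatment failures, it is reported by unblinded clinicians against no stated criteria, and it is analysed over all patients. Under-counting follows if any relapse falls outside the failure criteria, which the definition readily allows. How many do so cannot be read from the protocol.

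Unequal capture is a plausible risk, not an established bias. With an assumed 10-point gap and a true rate of 17.3% in both arms, a null odds ratio would appear as about 0.87 to 0.88 in one direction or 1.13 to 1.15 in the other, with false-positive risk rising from 5% to about 12%. The primary outcome and the sample size are unaffected. The change should be made, and it is best made while data are still being collected.

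**What to change.** 1. In section 3.6, ask the relapse question for every participant with a post-randomisation source control procedure, a re-admission or a treatment failure, whether or not failure was assigned. All three triggers are already collected.
2. Give short written criteria for relapse.
3. Where feasible, have the existing blinded endpoint committee classify relapse from the operative, radiology and microbiology reports.
4. In section 10.2.4, keep relapse over all patients as the outcome, and report relapse within treatment failure as a separate descriptive measure.

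The cost is one eCRF item and some added review, with no new tests. The review load across 1166 patients and 30 sites is not costed in the protocol, which is why item 3 is conditional. A relapse managed without any of the three triggers would still be missed, and the report should say so.

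If the restriction is intended, the minimum is to reconcile sections 3.6 and 10.2.4 by naming and interpreting the outcome as treatment failure with relapse.

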## 4 TRIAL DESIGN

A multicentre, open label, two-arm, parallel group, pragmatic, randomised controlled superiority trial with internal pilot. A total of 1166 consenting patients with cIAI will be recruited over 3 years and randomised on a 1:1 basis. Patients will be recruited from ICUs and hospital in-patient wards across 30 sites.

The EXTEND Trial protocol ISRCTN no. 72819021

## 4.1. Internal pilot

The EXTEND trial will incorporate a 12-month internal pilot phase which will assess setup and recruitment rates and monitor adherence with allocated antibiotic treatment durations. Site setup and recruitment will be assessed against the criteria given in the Table below (percentages indicate proportions recruited out of the end of pilot target). The thresholds in the "Green" column are based on reaching our recruitment target of 1166 in 36 months, assuming 30 sites are opened in a staggered manner over the first 24 months of the recruitment period. The thresholds in the "Red" column are based on the minimum values of these metrics for which (under certain assumptions) recruitment could still plausibly be completed in 36 months. Findings from the pilot phase will be used to remodel the projected recruitment trajectory for the main phase of the trial and, together with input from the trial oversight committees, inform any amendments necessary to achieve this trajectory. The trial team and oversight committees will also closely monitor the durations of antibiotics prescribed in each arm during the internal pilot phase. This will enable a proactive approach to managing and retraining sites where departures from the randomised allocations (as relates to antibiotic treatment durations) are identified and thereby ensure adequate separation of the two treatment groups. At the end of the internal pilot phase, the trial oversight committees and funder will review all elements of the pilot progression criteria, as well as data relating to adherence. They will advise whether the trial should; continue as planned or continue with minor or major amendments or enhanced monitoring/training, prior to making any recommendation on whether recruitment should be terminated early, if there is substantial evidence that the full trial is not feasible. Adherence to randomised allocation (standard and fixed-extended-duration antibiotic treatments) will be measured throughout the trial including in the internal pilot. Adherence rates will be reviewed at the end of the pilot phase.

	Red	Amber	Green
Recruitment rate (patients/site/month)	< 1.08	1.08 to 1.49	≥ 1.5
Number of sites opened	< 13 (< 65%)	13 to 20 (65% to 100%)	≥ 20 (≥ 100%)
Total number of participants recruited	< 144 (< 64%)	144 to 224 (64% to 100%)	≥ 225 (≥ 100%)
Separation (in days) between the average	< 5 days	5 to 10 days	> 10 days
antibiotic durations in treatment arms			

#### **Pilot progression criteria**

## 4.2 Study within a trial (SWAT)

We recognise the need to broaden participation in trials. We have experience within the team of developing illustrated narratives (picture story books) as a means of communicating messages around infection. We will conduct a SWAT to evaluate whether presentation of the study to potential participants using this re-designed, illustrated, narrative based PIS leads to an increased recruitment rate compared with presentation of the study using a standard PIS. We will work with the established

team which includes a writer ([name]) and illustrator ([name]), alongside our patient representatives, to co-design and study the "Effects of including a Picture Book with the Participant Information Sheet on trial recruitment and retention" (SWAT 166 MRC SWAT Repository Store). The SWAT will be cluster randomised at the site level to avoid contamination. Sites will be randomised 1:1 to either an enhanced PIS arm (Illustrated, narrative PIS + standard PIS) or standard PIS only arm. The allocation sequence will be generated by a researcher not involved in the recruitment of participants at sites. As is usual for embedded trials, no formal power analysis or sample size calculation was undertaken as the available sample size is dictated by the number of participants who are approached for consent. The primary outcome for this embedded trial is randomisation into the host trial. This outcome will be analysed at the individual level using a population averaged logit-binomial model (fit by generalised estimating equations) with a single binary indicator for SWAT allocation, and an exchangeable working correlation structure. The odds ratio for allocation will be reported together with a 95% confidence interval and p-value obtained using an appropriate small-sample adjustment. Further exploratory analyses will look at differences in retention between SWAT groups among those patients who are randomised into the host trial. The findings of the SWAT will be made publicly available as soon as possible after the end of the recruitment period. We will also collaborate with York Trials Unit who have completed a similar SWAT to ensure the data collected will facilitate future meta-analysis [24].

## 5 TRIAL SETTING

A list of the participating sites can be found at:

# https://www.google.com/maps/d/u/1/viewer?mid=1EwI01hfJZ042KVFrpAJgdrWUZOWyJVE&II=53.84928 164206432%2C-2.26273809999998z=5

Eligibility criteria for trial centres: Trial centres must be UK based hospitals whose patient population includes adults and have general or specialist abdominal surgical services on site.

Eligibility for individuals who will perform the interventions: All clinical staff involved in patient recruitment, randomisation and follow up must have current Good Clinical Practice (GCP) training. They must also complete study specific training, and either the HRA eLearning module "Research involving participants lacking mental capacity" or provide evidence of Mental Capacity Act (MCA) training completed e.g. mandatory training completed as part of clinical duties within their NHS Trust'.

## 6 PARTICIPANT ELIGIBILITY CRITERIA

#### 6.1 Inclusion criteria

- Adults (≥ 16 years) with cIAI (see cIAI definition)
- Being treated with antibiotics until the point of randomisation, but within 10 days of initiation of effective antibiotic treatment for cIAI
- Ability to provide informed consent by the patient or their consultee
- More than 72 hours of further active in-patient management for the patient's cIAI is required
- In the event that the patient is re-admitted to hospital during the trial period, they are likely to be admitted to a hospital participating in the EXTEND trial

Patients will be included in the trial whether or not they undergo surgical or radiological source control procedures.

 cIAI is defined by the following case definition:

- A clinical presentation consistent with cIAI, plus
- Fever (temperature of ≥ 37.8°C) and/or a neutrophilia (> 7.5×10^9/L) and/or neutropaenia (<1.8x109/L) and/or intestinal pathogens cultured from sterile sites (closed peritoneum or blood) around the time of cIAI diagnosis, plus

- Evidence of pathologic findings on radiologic examination, or
- Evidence of pathologic findings at operation

 The first day of effective antibiotic treatment will be determined by the patient's clinical team or clinical research team. Antibiotics that do not count towards these 10 days of effective treatment are:

- Antibiotic prophylaxis e.g., penicillin for splenectomy, elective surgery antibiotic prophylaxis, UTI prophylaxis
- Treatment for other infections that is not effective for cIAI e.g., cystitis. Antibiotics that are often used for cystitis and aren't effective for cIAI include Cephalexin, Fosfomycin Trimethoprim, Nitrofurantoin, and Pivemecllinam
- Oral antibiotics prescribed to treat infection prior to hospitalisation
- Previous courses of treatment antibiotics: A previous course is one stopped for 48 hours or more

 The further 72 hours starts from the first day of effective antibiotic treatment i.e., for a patient admitted to hospital with a cIAI, 3 days of admission are needed. Where a patient is already in hospital e.g., a post operative patient, a further 3 days of admission are required starting from the point of the first day of effective antibiotic treatment.

